8.4 SAFETY AND OTHER ASSESSMENTS

8.4.1 CONCOMITANT MEDICATION REVIEW

Concomitant medications will be reviewed at every visit as indicated in SOA (section 1.3).

8.4.2 CLINICAL LABORATORY ASSESSMENTS

Clinical labs will be performed centrally as indicated in SOA (section 1.3) and will consist of Hematology, Chemistry Panel, TSH, Vitamin B12, and urinalysis. Lab reports will be reviewed, signed and dated by the site Principal Investigator (or a medically-qualified individual delegated by the PI). If a value is outside of the laboratory's normal range, the clinician will indicate if it is clinically significant or not. Those results that are deemed clinically significant may need to be repeated and follow up with the participant's primary care physician for further evaluation should occur.

If a participant is having lumbar puncture, a coagulation panel and platelet count will be obtained either locally or centrally prior to the LP (within 3 months), in order to rule out a clotting disorder.

If a female is not surgically sterile or post-menopausal by two years, a pregnancy test will be performed locally at the site prior to conducting the PET scan. Participants with positive pregnancy test will be ineligible for amyloid PET imaging.

8.5 ADVERSE EVENTS AND SERIOUS ADVERSE EVENTS

8.5.1 DEFINITION OF ADVERSE EVENTS

An adverse event (AE) is defined as any untoward medical occurrence. Adverse events deemed related to the study compounds (e.g. PET tracers) or procedures by the site investigator and serious adverse events occurring within 2 days of PET tracer administration, regardless of causality, will be tracked during the study.

The following events are considered adverse events:

- (1) worsening or change in nature, severity, or frequency of conditions or symptoms present at the start of the study

- (2) participant deterioration due to primary illness
- (3) intercurrent illness
- (4) drug interaction

Abnormal laboratory and imaging findings will only be reported as an AE if the PI or medical designee considers it to be clinically significant or if it leads to the participant being withdrawn from the study.

The investigator should attempt to establish a diagnosis of the event based on signs, symptoms, and or other clinical information. In such cases, the diagnosis should be documented as the AE and not the individual signs or symptoms. Symptoms and conditions present at the beginning of the study will be characterized, so that AEs can be defined as any new symptom, or any increase in frequency or severity of an existing symptom. Adverse events should be described with medical terminology so that the event can be matched against a medical coding dictionary, such as Medical Dictionary for Regulatory Activities (MedDRA).

Investigators should report their assessment of the potential relatedness of each AE to the protocol compounds and procedures. Following questioning and evaluation, only AEs, determined to be related to the protocol compounds or procedures by a medically qualified Site PI or medical designee or serious adverse events occurring within 2 days of PET tracer administration, regardless of causality, must be documented in the participant's records, in accordance with the investigator's normal clinical practice, and on the AE eCRF.

8.5.2 DEFINITION OF SERIOUS ADVERSE EVENTS (SAE)

A serious adverse event is defined as an adverse event or suspected adverse reaction that results in any of the following outcomes:

1. Death
2. A life-threatening adverse event
3. In-patient hospitalization or prolongation of existing hospitalization (see below for more information regarding hospitalization)
4. A persistent or significant incapacity or substantial disruption of the ability to conduct normal life functions
5. A congenital anomaly/birth defect

Important medical events that may not result in death, be life-threatening, or require hospitalization may be considered serious when, based upon appropriate medical judgment, they may jeopardize the participant and may require medical or surgical intervention to prevent one of the outcomes listed in this definition. Examples of such medical events include allergic bronchospasm requiring intensive treatment in an emergency room or at home, blood dyscrasias or convulsions that do not result in inpatient hospitalization, or the development of drug dependency or drug abuse.

Hospitalizations that fulfill one of the following conditions will not have to be reported as SAE:

- Admission for treatment of a pre-existing condition that is not associated with the development of a new AE or with a worsening of the pre-existing condition (i.e., work-up for persistent lab abnormality that occurred prior to the study)
- Social admission (i.e., participant has no place to sleep)
- Administrative admission (i.e., yearly physical exam)
- Protocol-specified admission (i.e., for a procedure required by the study protocol)

- Optional admission not associated with a precipitating clinical AE (i.e., pre-planned treatments, elective cosmetic surgery)

For more detail, refer to the Code of Federal Regulation Title 21 Part 312:

<http://www.accessdata.fda.gov/scripts/cdrh/cfdocs/cfcfr/cfrsearch.cfm?fr=312.32>

8.5.3 CLASSIFICATION OF AN ADVERSE EVENT (AE)

Reporting standards for reporting AEs will be provided in the relevant procedures manual and must be followed regardless of applicable regulatory requirements that may be less stringent.

8.5.3.1 SEVERITY OF EVENT

All AEs will be assessed by the study clinician using a protocol defined grading system. The following guidelines will be used to describe severity.

- **Mild** – Events require minimal or no treatment and do not interfere with the participant's daily activities.
- **Moderate** – Events result in a low level of inconvenience or concern with the therapeutic measures. Moderate events may cause some interference with functioning.
- **Severe** – Events interrupt a participant's usual daily activity and may require systemic drug therapy or other treatment. Severe events are usually potentially life-threatening or incapacitating. Of note, the term "severe" does not necessarily equate to "serious".

8.5.3.3 EXPECTEDNESS

An AE or suspected adverse reaction is considered "unexpected" if it is not listed in the IB, package insert, or device labeling or is not listed at the specificity or severity that has been observed; or, if an IB is not required or available, is not consistent with the risk information described in the protocol, as amended.

8.5.4 TIME PERIOD AND FREQUENCY FOR EVENT ASSESSMENT AND FOLLOW-UP

Adverse events will be reported from the time of signing the TRC informed consent until signing an ICF for a clinical trial, and will resume following completion of the trial and reactivation in TRC.

Following up on AEs: The investigator is obliged to follow participants with AEs until the events have resolved, the conditions are considered medically stable, or the participants are no longer available for follow up. Participants who discontinue due to adverse experiences will be treated and followed according to established medical practice. All pertinent information will be entered into the eCRF.

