7.1.1 CLINICAL TRIAL PARTICIPATION

Participants who screen into clinical trials will be placed in temporary inactive status in TRC-PAD at the time of consent into the clinical trial, the participant would return to active status following completion of participation in the trial (see Section 5.4).

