8.1.3 ACTIVE STUDY PHASE (ONGOING 6-MONTH ASSESSMENTS)

The remaining study procedures will be conducted as outlined in Schedule of Activities (section 1.3). Timing of each follow-up visit is calculated from the start of screening. Procedures for each visit may be completed over multiple days but must occur within the window of +/-21 days from the visit's target date.

Screening visit procedures may be repeated at follow-up visits, with approval from the Coordinating Center, if needed to assess potential changes in eligibility for clinical trials, e.g. after participation in a clinical trial or prolonged enrollment in TRC without successful enrollment in a trial.

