8.5.6 SERIOUS ADVERSE EVENT REPORTING

Serious adverse events deemed related to the study compounds (e.g. PET tracers) or procedures by the Site PI or occurring within 2 days of PET tracer administration, regardless of causality, will be tracked during the study. Any serious adverse event meeting either requirement which occurs during the course of the investigation (i.e. any time after informed consent) or within 30 days of last study visit must be reported to the Medical Monitor at ATRI within 24 hours of learning of the event. ATRI Medical Safety team will generate an SAE report, which will be distributed to all participating sites and to the central IRB.

All serious adverse events (SAEs) will be followed until satisfactory resolution or until the site investigator deems the event to be chronic or the participant is stable. Other supporting documentation of the event may be requested by ATRI's Medical Safety group and should be provided as soon as possible.

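### Section 8.5.4 stops adverse event reporting at a clinical-trial consent but Section 8.5.6 does not, so a qualifying SAE that starts after that consent falls under contradictory rules

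*Combined protocol and SAP*

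**What the plan says.** The combined protocol and SAP sets the reporting period in two places, and several other sections bear on it.

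- **Section 8.5.4**, which is headed as the time period for event assessment, says "Adverse events will be reported from the time of signing the TRC informed consent until signing an ICF for a clinical trial". Reporting then "will resume following completion of the trial and reactivation in TRC". The same section obliges the investigator to keep following events already under way.
- **Section 8.5.6** covers SAEs that the site PI judges related to study compounds or procedures, and SAEs "occurring within 2 days of PET tracer administration, regardless of causality". A qualifying SAE that "occurs during the course of the investigation (i.e. any time after informed consent) or within 30 days of last study visit" is one that "must be reported to the Medical Monitor at ATRI within 24 hours of learning of the event". The section does not mention a trial consent.
- **Section 8.5.2** defines an SAE as an adverse event, or suspected adverse reaction, with one of the listed serious outcomes.
- **Sections 8.5.1 and 8.5.5** say that adverse events related to TRC compounds or procedures are to be documented on the AE eCRF and tracked. Neither has a cut-off at trial consent.
- **Sections 5.4 and 7.1.1** say that participants entering a trial "will be placed in temporary inactive status in TRC-PAD at the time of consent into the clinical trial" and become active again afterwards. Neither says what happens to safety reporting in between.
- **Section 8.1.3** and footnote 8 of the Schedule of Activities allow screening procedures, which include amyloid PET or LP, to be repeated with Coordinating Center approval "if needed to assess potential changes in eligibility for clinical trials, e.g. after participation in a clinical trial or prolonged enrollment in TRC".

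**The concern.** The stop in 8.5.4 is tied to signing a form, not to the time since a tracer or a lumbar puncture. TRC exists to move people into trials, so a trial consent is the expected next step, and a TRC scan or LP may come before it. A site that learns of an SAE from a TRC procedure after the trial consent has two instructions: reporting has stopped, and a report is due in 24 hours.

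At stake are prompt notice to the Medical Monitor and a complete record of harms from TRC's own tracers and procedures. Section 10.1.6 promises the DSMB all adverse events and SAEs, but the DSMB can see only what sites report. Non-serious events matter too: Section 2.3.1.2 expects headache in about 5% of elderly people after LP and persistent low-pressure headache in about 1-4% of participants. Section 8.1.2.2 requires a call within 72 hours of PET or LP to ask about adverse events. If the trial consent comes before the call, the site must ask about events that 8.5.4 no longer has it report.

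**Working it through.** No power, sample size or event count is involved, so the check is a comparison of the rules. Let a TRC PET or LP take place on day 0, let the trial consent be signed on day d, and let an event start on day t.

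| Event | Section 8.5.4 | Section 8.5.6 | Result |
|---|---|---|---|
| SAE related to a TRC compound or procedure, t after d | Reporting stopped | Due in 24 hours | Contradiction |
| SAE of any cause within 2 days of tracer, t after d | Reporting stopped | Due in 24 hours | Contradiction, only if the consent is signed inside the 2-day window |
| Related non-serious event, t after d | Reporting stopped | Not covered | Gap, at odds with 8.5.1 and 8.5.5 |
| Reportable event that started before d | Reported, and followed up | Reported if a qualifying SAE | No conflict |
| Unrelated SAE outside the 2-day window, t after d | Reporting stopped | Does not qualify | No conflict |

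**Does the 8.5.4 stop reach SAEs?** On its face, yes. Section 8.5.2 makes an SAE a kind of adverse event, and the 8.5.4 heading speaks of events in general. It contains no exception for serious ones.

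**Does 8.5.6 stop at a trial consent?** No. Its window has two alternatives: any time after informed consent, or within 30 days of the last study visit. A trial consent comes after the TRC consent, so the first alternative is met whatever the second means.

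**Does another section settle it?** No. Sections 5.4 and 7.1.1 change the participant's status to temporarily inactive without assigning a reporting rule. Nothing gives 8.5.4 or 8.5.6 precedence.

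**Worked case (assumed dates).** LP on day 0, trial consent on day 5, LP-related SAE on day 10. Under 8.5.4 the event falls in the suspended period. Under 8.5.6 it is after informed consent and related, so it is due within 24 hours of the site learning of it. If the day-10 event is instead a first, non-serious post-LP headache, 8.5.6 does not apply and 8.5.4 cuts it off.

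**How long does the conflict last?** For a related SAE, the first alternative in 8.5.6 carries it through the whole inactive period. The documents give no trial duration, so no number of days can be attached. For an SAE of any cause after a scan, it lasts at most to the end of the 2-day window.

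**The case against.** The strongest reply is that 8.5.6 is the specific rule for SAEs and overrides the general sentence in 8.5.4, so no qualifying SAE is lost. That is a fair reading, but the protocol does not state it. A site that follows the section on time period could reasonably stop reporting. The reading also leaves the related non-serious event cut off.

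A second reply points to other routes. Section 8.6.2 sends unanticipated problems to the IRB and Coordinating Center within 24 hours with no stop at trial consent, and the 72-hour call may bring an event to light. These help only in part. Section 8.6.1 requires an unanticipated problem to be unexpected, and a post-LP headache is a risk the protocol already describes. The call finds an event; it does not settle whether the event is reportable.

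A third reply is that the sequence may be rare. Repeat procedures need Coordinating Center approval, PET and CSF results are generated centrally, and a repeat done to judge trial eligibility would ordinarily await its result. For a first screening, 5.4 concerns people already enrolled in TRC, after central review and Stage 3 authorization. This stands as a limit on size: a consent within 2 days of a scan in particular is not shown to be realistic. It does not remove the conflict.

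**Conclusion.** The point holds with a defined scope. The direct contradiction covers qualifying SAEs with onset after the trial consent. For related non-serious events, 8.5.4 imposes a cut-off that does not sit with 8.5.1 and 8.5.5. Events that began before the consent remain under follow-up. The frequency is not given and may be small. The conclusion assumes only that 8.5.4 means adverse events to include SAEs, as 8.5.2 implies.

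A reader might infer more, and the documents do not support it:

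- **That the mismatch is 30 days minus the days since the last TRC visit.** This ignores the first alternative in 8.5.6. It also treats the latest visit as the last one, although the participant is only temporarily inactive.
- **That the plan encourages trial consent soon after a procedure.** No text sets any timing between the two.
- **That such events will be misattributed in the receiving trial.** That depends on protocols not available here.
- **That the AE eCRF is closed to inactive participants.** No section says so, and 5.4 has trial screening and participation data entered in the eCRF.

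**What to change.** Reconcile 8.5.4 with 8.5.6:

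1. State in 8.5.4 that the stop at a trial consent does not apply to events related to a TRC tracer or procedure, or to SAEs within the 2-day post-tracer window.
2. State in 8.5.4 that SAE reporting follows the window in 8.5.6.
3. Define the last study visit for participants on temporary inactive status.

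The new text should not cap reporting at 30 days after the latest TRC visit. A related SAE on day 35 is after informed consent and so is reportable under 8.5.6 now; a cap would remove it. Because the documents do not show which window was intended, the sponsor should confirm the reconciled rule and carry it into 5.4 and 7.1.1 by cross-reference.

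The cost is two sentences in 8.5.4, one definition and the cross-references. The downside is that a few events will be reported to both TRC and the receiving trial.

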8.5.5 ADVERSE EVENT REPORTING

Adverse events deemed related to the study compounds (e.g. PET tracers) or procedures by the Site PI will be tracked during the study. The principal investigators and ATRI staff will monitor the study procedures for this study for overall safety and scientific relevance on an ongoing basis. The local site PI (in conjunction with, as needed, the Medical Monitor and the data safety monitoring board (DSMB)) will evaluate each serious adverse event for safety and causality and will determine whether the adverse event affects the risk/benefit ratio of the study and whether modifications to the protocol or consent form are required.

8.5.6 SERIOUS ADVERSE EVENT REPORTING

Serious adverse events deemed related to the study compounds (e.g. PET tracers) or procedures by the Site PI or occurring within 2 days of PET tracer administration, regardless of causality, will be tracked during the study. Any serious adverse event meeting either requirement which occurs during the course of the investigation (i.e. any time after informed consent) or within 30 days of last study visit must be reported to the Medical Monitor at ATRI within 24 hours of learning of the event. ATRI Medical Safety team will generate an SAE report, which will be distributed to all participating sites and to the central IRB.

All serious adverse events (SAEs) will be followed until satisfactory resolution or until the site investigator deems the event to be chronic or the participant is stable. Other supporting documentation of the event may be requested by ATRI's Medical Safety group and should be provided as soon as possible.

8.5.7 REPORTING EVENTS TO PARTICIPANTS

Study participants at an aggregate level will be informed by the Investigator or designated site clinician as deemed clinically necessary by ATRI.

8.5.8 EVENTS OF SPECIAL INTEREST

N/A

8.5.9 REPORTING OF PREGNANCY

Pregnancy is not an adverse event, but some studies will require unique considerations if pregnancy was to occur during the study. A participant who is enrolled in the TRC cohort who becomes pregnant can continue in the cohort but eligibility for enrollment in to a preclinical/prodromal AD trial will occur once pregnancy (and any interval of breast feeding) are complete.

8.6 UNANTICIPATED PROBLEMS

8.6.1 DEFINITION OF UNANTICIPATED PROBLEMS (UP)

The Office for Human Research Protections considers unanticipated problems involving risks to participants or others to include, in general, any incident, experience, or outcome that meets all of the following criteria:

- Unexpected in terms of nature, severity, or frequency given (a) the research procedures that are described in the protocol-related documents, such as the IRB approved research protocol and informed consent document; and (b) the characteristics of the participant population being studied
- Related or possibly related to participation in the research (“possibly related” means there is a reasonable possibility that the incident, experience, or outcome may have been caused by the procedures involved in the research).
- Suggests that the research places participants or others at a greater risk of harm (including physical, psychological, economic, or social harm) than was previously known or recognized.

ATRI Coordinating Center staff will monitor the unanticipated problems for overall safety and scientific relevance on an ongoing basis and provide information to the Data Safety Monitoring Board.

8.6.2 UNANTICIPATED PROBLEM REPORTING

The investigator will report unanticipated problems (UPs) to the reviewing Institutional Review Board (IRB) and to the Coordinating Center via the AE eCRF. The UP report will include the following information:

- Protocol identifying information: protocol title and number, PI’s name, and the IRB project number;
- A detailed description of the event, incident, experience, or outcome;
- An explanation of the basis for determining that the event, incident, experience, or outcome represents an UP;
- A description of any changes to the protocol or other corrective actions that have been taken or are proposed in response to the UP.

To satisfy the requirement for prompt reporting, UPs will be reported using the following timeline:

- UPs that are serious adverse events (SAEs) will be reported to the IRB and to the Coordinating Center within 24 hours of the investigator becoming aware of the event.
- Any other UP will be reported to the IRB and to the Coordinating Center within 24 hours of the investigator becoming aware of the problem.
- All UPs should be reported by the site to appropriate institutional officials (as required by an institution’s written reporting procedures), upon receipt of the report of the problem from the investigator.

8.6.3 REPORTING UNANTICIPATED PROBLEMS TO PARTICIPANTS

Participants will be informed by the Investigator or designated site clinician as deemed clinically necessary by the Coordinating Center.

8.7 GLOBAL UNIQUE IDENTIFIER

A Global Unique identifier (GUID) will be generated for each participant if permissible based on local and regional laws/requirements. A GUID provides a method to link collections of research data and specimens, balancing the competing goals of distinguishing individuals, collecting accurate information for matching, and protecting confidentiality. Certain personal identifying information (PII) is collected by the site and submitted to an algorithm to create the GUID, which will then be recorded in the CRF. The PII fields employed in this approach are invariant over the lifetime of the subject. This approach has proven to adequately discriminate individuals in both simulation and field studies (Johnson et al., 2010). Software will be provided to sites to generate the GUID using a standard algorithm so that the PII itself will not be submitted or stored centrally.

